We expect to enroll between 30-50 patients based on eligibility over 2.5 years of recruitment. This estimate is based on the most recent hospital admissions data since the start of the COVID-19 pandemic estimating approximately 100 patients will qualify for the study over 2.5 years. Participants will be randomized 1:1 to receive the intervention. Recruitment and retention will be assessed during the trial as outcomes.

b. Inclusion and Exclusion Criteria

Children \geq 6 years and <19 years of age admitted with TBI (defined as injury to the head from external forces with severity mild, moderate, or severe classified by Glasgow Coma Scale) will be included.

Children under the age of 6 years will be excluded due to increased variability in baseline sleep patterns, daytime napping, and lack of standardized tools identifying sleep outcomes between children younger and older than 6 years. Patients over age 18 years will be excluded as they are primarily treated in adult care units and the study focus is pediatric. Patients unable to tolerate enteral medications within 72 hours of hospital admission, as defined by the clinical care Attending Physician, will be excluded from the study. Patients undergoing dialysis, requiring extracorporeal life support, or with significant liver dysfunction (defined as aspartate aminotransferase (AST) or alanine aminotransferase (ALT) more than 2 times the upper limit of normal for age) will be excluded. Patients about whom the Attending Physician has any safety

concerns regarding use of melatonin as per clinical judgement will be excluded from the study. Patients with abusive trauma will be excluded. Suspected or known prisoners are excluded. Pregnant patients are excluded. There will be no requirement for contraception during the trial in female patients of child-bearing age. Patients must have a parent or guardian with whom they reside in order to participate in the study given the parent-reported measures used for outcomes.

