Screening: Children with traumatic brain injury (TBI) will be screened for inclusion in the study by the Trauma Research Group (TRG) on admission to Oregon Health and Science University or Doernbecher Children's Hospital. Research coordinators with the TRG are available to screen all TBI admissions for inclusion into active research studies 24 hours per day. Screening activities will take place under a HIPAA waiver per the "Activities Preparatory to Research" policy at OHSU. Given the extensive experience and training of the TRG, we expect very few if any screen failures of TBI admissions, and this will be actively monitored throughout the study period.

Recruitment Procedures: Recruitment will be maximized by using consistent trained staff within the TRG that have extensive experience consenting subjects and surrogates for research, including critically injured children. The recruitment process will be overseen by [name], a Pediatric Critical Care physician, with expertise in caring for critically injured children. TRG staff

are trained and mindful of the critical nature of traumatic brain injury and will ensure the appropriate time and conditions for obtaining informed consent. Individual staff are monitored to ensure adherence to TRG standard operating procedures and study protocols.

The appropriate time to approach patients will be determined by study staff and clinical care staff, and consent will be obtained within 72 hours of Pediatric Intensive Care Unit admission to ensure starting the intervention as early as possible. Delaying consent for critically ill patients will not adversely affect the study outcomes, but will allow for acute stabilization of patients prior to consideration of study inclusion, ensure ability to administer enteral medications, and to allow for determination by the primary clinical care team of a patient's likelihood of survival. Consent procedures will be reviewed at least quarterly during TRG coordinator meetings to ensure ongoing consistency. The minimum goal set for recruitment is 50% of eligible patients.

Retention: All patients consenting for inclusion will have phone, address, email contact information collected at time of consent. Outcomes will be obtained at 1-month follow-up as described.

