Text messaging will be used for system generated reminder prompts such as "Please sync your device"; or if battery is low, "Please charge your battery" during the 1-month study period while participants wear the Fitbit. Text messaging functions require sharing of participant phone numbers with the Fitabase platform and Twilio, Inc.

Feasibility benchmarks will be assessed every 6 months during the trial. If feasibility benchmarks are not met, study procedures and the protocol will be reviewed using input from stakeholders and preliminary data to determine if changes are warranted.

Table 1. Outcomes Evaluation and Analysis for Melatonin Trial

Outcome (time collected)	Measurement or Assessment Tool	Analysis
Feasibility Outcomes		
*Recruitment (6-monthly feasibility reviews)	Number subjects consented/approached; goal >50%	Descriptive percent
*Retention (6-monthly feasibility reviews)	Quantitative Number completed/consented; Goal >90%	Descriptive percent
Screen failure (6-monthly feasibility reviews)	Number approached/eligible patients; expect <<5%; eligible patients will be derived from the OHSU Trauma Registry and compared to study logs	Descriptive percent
Reasons for Participation/ Non-participation (time of approach/consent)	Qualitative response to survey: "Please describe reasons you chose [not to or to] participate in this research study"; "Could the study team do something different in the future to increase chances you would participate in future studies?"	Thematic analysis
Reasons for drop-out (30-day)	Qualitative response to survey: "We would like to know how we can improve our study in the future. Please tell us your reasons for leaving the trial"; "How could the study team have assisted you better in completing the trial?"	Thematic analysis
Adherence (30-day)	Pill counts: adherent if \geq 75% prescribed pills are taken at the follow-up study visit; will be counted as unknown if pill count not available Sleep tracking usage: actigraphy data and sleep diaries will be compared to age based recommendations; actigraphy counted as	Descriptive percent; Chi-square to compare intervention arms Descriptive percent; Chi-square to compare intervention arms

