	
adherent if device worn for ≥5 nights consecutively; we will assess sleep routines through actigraphy; will be counted as unknown if did not participate in the actigraphy portion
 
Quantitative survey: "How many nights each week did you take the study medication since discharge?"
 
None, 1-3, 3-4, 5-7, All
 
Quantitative survey response: "Did you receive sleep education with your hospital discharge paperwork?"; choices of a) did not receive discharge paperwork; b) I did not receive any sleep education at discharge; c) I received it, but did not use it; d) I received it, but did not find it helpful; e) I received it, and found it helpful; responses to this question will also be compared with the discharge instructions within the electronic health record to determine if the resource was provided as intended.
	Descriptive percent; Chi-square to compare intervention arms
Acceptability Outcomes		
*Adverse Events (discharge, 30-day)	
Qualitative response to survey: "Did you have any new medical problems since the last study visit?"
 
Quantitative yes/no response: "Did you have any of the following symptoms since the last visit"
 
 a. Nausea b. Vomiting c. Diarrhea d. Drowsiness e. Fatigue f. Headache g. Behavioral changes h. Vivid dreams i. Nightmares j. Waking up at night k. Itchy skin l. Rash m. Appetite changes n. Bodily pain or aches o. Chest pain p. Enuresis or bedwetting q. Dizziness r. Tinnitus or ringing in the ears s. Feeling cold 
Evaluation of medical record, patient assessments to quantify adverse events and unexpected problems collected as a dichotomized yes/no and number of events
	
Thematic analysis
 
Descriptive percent and mean with standard deviation; Chi-square (yes/no) and Mann-Whitney U test (continuous) to compare intervention arms

Satisfaction (30-day)	Quantitative rankings on a likert scale survey: experiences with the study overall, consent process, study team, study intervention, questionnaires, Actigraphy devices, care received	Descriptive median and interquartile range; Mann-Whitney U tests

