a. Sharing of Results with Subjects

Data from this clinical trial will not be shared directly with participants. The results of the clinical trial and de-identified data will be made in accordance with NIH regulations and clinicaltrials.gov.

b. Data and Specimen Banking

No specimens will be stored. Study records will be retained for the longest regulatory retention period. After that time, records will be destroyed in a confidential manner.

8. Data Analysis

See Table 1 for outline of data analysis planned for study outcomes. As this is a pilot intervention trial, the focus will be on feasibility and acceptability of the pragmatic intervention trial. We will also explore effectiveness outcomes, but recognized we will be underpowered for a definitive effectiveness trial within this heterogeneous population selected to be representative of the population of interest. We will use our pilot trial to inform a future larger trial that will include longitudinal real world health outcomes relevant to the pediatric TBI population if supported by our preliminary results.

Prior to evaluating outcomes, we will perform a thorough descriptive analysis of participant baseline characteristics (age, race, ethnicity, gender, pre-injury comorbidities, TBI characteristics including severity, location, and type). We will examine patterns of missingness in our outcomes collected at 1-month, differences in participant and non-participant characteristics, and differences in participants who completed versus dropped out of the study to ascertain potential bias. Additionally, we will describe and compare the distribution of patient and clinical characteristics, including age and TBI severity, across treatment groups to ensure our randomization protocol was successful. Comparisons between groups will be made using chi-square tests for categorical variables. Depending on characteristics of the data, t-tests and Mann-Whitney U tests will be used to compare continuous variables between groups. We plan to perform both intention to treat and per protocol analyses.

Quantitative feasibility outcomes will be presented as a percentage of patients, the denominators of which are listed in Table 1. Comparisons between groups will be made with chi-square tests.

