Quantitative acceptability outcomes for adverse events will be dichotomized to yes/no and evaluated as a total number for each patient summarized using percent and median with interquartile range (IQR), respectively. Acceptability outcomes for satisfaction will be measured using Likert scales for which we will present results as medians and IQR. Chi-square tests will be used to compare dichotomized outcomes between treatment groups, and Mann-Whitney U tests will be used to compare total number of events. Effectiveness outcomes will be summarized using means and standard deviations, except for daytime sleep episodes which will be summarized as a median and IQR; these outcomes will be summarized for the overall study population and by treatment group. We will primarily examine the effectiveness of our intervention using linear regression to assess differences in the total SDSC score across treatment groups at 1-month. Linear regression will allow us to assess differences in effectiveness outcomes while controlling for covariates that may confound this relationship; covariates of particular interest will include age and TBI characteristics. Covariates identified in our initial descriptive analysis as significantly different between treatment groups, and covariates significantly associated with SDSC total score in bivariate analyses will also be explored with multiple linear regression.

Secondary effectiveness outcomes that specifically evaluate sleep phenotypes (measured by questionnaire and actigraphy) will be similarly evaluated with linear regression, except daytime sleep episodes which will be modeled using a count model, such as Poisson or negative binomial regression. For these secondary effectiveness outcomes, our focus is the magnitude of the association rather than statistical significance, as multiple comparisons will be made. Our primary goal with this secondary analysis will be to determine if the intervention appears effective for particular phenotypes that could be targeted in future studies. Results of these secondary analyses will be used as estimates for effect sizes in future intervention study design.

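### Adverse events are a primary outcome, but the arms are compared only by chi-square and Mann-Whitney tests, with no difference estimate, confidence interval or upper bound, at 15 to 25 children per arm

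*Combined protocol and SAP*

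**What the plan says.** The Outcomes paragraph of section 6 names adverse events, with utilization, as the quantitative measures of acceptability, and Table 1 stars adverse events as primary. The data are a yes/no list of 19 symptoms, an open question on new medical problems, and events found by record review and patient assessment, recorded as yes/no and as a number.

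Table 1 gives the comparison as "Chi-square (yes/no) and Mann-Whitney U test (continuous) to compare intervention arms". Section 8 repeats it: "Chi-square tests will be used to compare dichotomized outcomes between treatment groups, and Mann-Whitney U tests will be used to compare total number of events". Descriptive summaries are also planned: percentages, plus mean and standard deviation in Table 1 or median and interquartile range in section 8. Neither place mentions a difference between arms, a confidence interval, an upper bound or an acceptable level of events. Recruitment and retention, by contrast, have numeric goals in Table 1 (above 50% and above 90%).

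On sample size, section 5a states: "We expect to enroll between 30-50 patients based on eligibility over 2.5 years of recruitment", and "Participants will be randomized 1:1 to receive the intervention". On power, section 8 says that the investigators "recognized we will be underpowered for a definitive effectiveness trial". It also puts magnitude ahead of significance, but for secondary effectiveness outcomes only. Neither statement covers adverse events.

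**The concern.** For an effectiveness outcome, a small trial that finds nothing gives a disappointing result. For harm the error runs the other way: a missed difference looks reassuring. A comparison whose only inferential product is a p-value therefore needs an estimate beside it, most of all for a primary outcome in a small sample. Without one, the report would not state how large an excess of events on melatonin remains compatible with the data. Those planning the larger trial would need that figure. The plan already applies this reasoning to its secondary effectiveness outcomes but not to adverse events.

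**Working it through.** **Inputs from the documents.** About 100 eligible patients (section 5a: "estimating approximately 100 patients will qualify for the study over 2.5 years"); a recruitment goal of half (section 5e: "The minimum goal set for recruitment is 50% of eligible patients"); 1:1 allocation; a retention goal above 90% (Table 1: "Quantitative Number completed/consented; Goal >90").

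**The plan's own figure.** 100 × 0.50 = 50 reproduces the upper end of the enrolment range. The lower end of 30 has no stated inputs, and no power or detectable difference for adverse events is given. Per arm: 30/2 = 15 and 50/2 = 25. With 10% loss: 27/2 = 13.5 and 45/2 = 22.5.

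**Assumptions, because the documents are silent.** Two-sided 5% level; control event rates from 5% to 75%; a true excess of 20 percentage points, or 0.5 standard deviations for counts; chi-square without continuity correction, with the Yates version also shown.

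**1. Chance of missing a 20-point excess.** With a of n children affected on melatonin and b of n on placebo, Pearson's statistic is 2n(a − b)² / [(a + b)(2n − a − b)]. Yates replaces |a − b| by |a − b| − 1 (not below zero). Adding the two binomial probabilities over all tables with p ≥ 0.05 gives the exact miss rate. Cells show uncorrected / Yates, in percent.

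| Placebo vs melatonin | 15 per arm | 20 per arm | 25 per arm |
|---|---|---|---|
| 5% vs 25% | 68.8 / 91.0 | 55.6 / 77.3 | 44.5 / 69.0 |
| 10% vs 30% | 72.2 / 89.3 | 64.3 / 78.1 | 55.0 / 72.9 |
| 20% vs 40% | 76.7 / 89.5 | 70.9 / 82.4 | 64.8 / 77.1 |
| 30% vs 50% | 80.5 / 90.4 | 75.5 / 85.8 | 66.6 / 76.8 |
| 40% vs 60% | 81.7 / 90.5 | 77.8 / 86.8 | 66.4 / 76.3 |

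The table is symmetric: 75% vs 95% equals 5% vs 25%. Only at the boundary is detection likely: 0% vs 20% at 25 per arm is missed in 1 − 0.766 = 23% (uncorrected). For 80% power the usual formula needs 62 per arm (10% vs 30%) to 93 per arm (30% vs 50%).

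**2. Event counts.** For a 0.5 SD shift, simulated Mann-Whitney power with normal data is 0.24 at 15 and 0.39 at 25 per arm, so the shift is missed in 76% and 61% of trials. With skewed counts the figures are 81% and 72%.

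**3. What an interval would show.** The Newcombe interval combines the two Wilson intervals (l, u). Its lower limit is d − √[(p₁ − l₁)² + (u₂ − p₂)²] and its upper limit is d + √[(u₁ − p₁)² + (p₂ − l₂)²].

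- 20% observed in both arms (no excess): the 95% interval is ±28 points at 3/15 each, ±25 at 4/20 each and ±22 at 5/25 each.
- 9/25 vs 4/25 (20-point excess): statistic 50 × 25 / (13 × 37) = 2.60, p = 0.11; interval −4 to +42 points.
- 15/25 vs 10/25 (20-point excess): statistic 50 × 25 / (25 × 25) = 2.00, p = 0.16; interval −7 to +44 points.

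**4. No serious events in an arm.** The exact one-sided 95% upper bound is 1 − 0.05^(1/n): 18% for n = 15 and 11% for n = 25.

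**The case against.** The strongest reply is that this is a single-centre pilot, that low power in a pilot is not an error, and that no power for adverse events is claimed. That is right: the sample size is not the fault. It is the reason to report estimates with intervals beside the tests.

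A reader might infer that a non-significant test is meant to stand in for acceptability. The documents do not support that. Nowhere do they say that a p-value decides acceptability or that the larger trial depends on this test. Acceptability also draws on utilization, satisfaction, reasons for non-adherence and thematic analysis. Section 10 gives the monitoring board cumulative serious events by arm, and a separate monitoring plan, not available here, may hold further criteria. These sources matter, but none of those described puts a limit on the excess of non-serious events at the end of the trial.

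Percentages are planned, and if they are shown by arm anyone can derive an interval from them. This also stands: no information is lost, and the gap is one of reporting.

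The miss rates depend on assumed event rates. With 19 symptoms asked of children just admitted with brain injury, very high rates are plausible, and at 75% versus 95% with 25 per arm the uncorrected test misses slightly fewer than half. So it is not true that non-significance is the likely result in every plausible case.

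Finally, one might want acceptability judged on the upper confidence limit. The plan sets no margin, and even with identical observed rates of 20% the limit is +22 to +28 points, so such a rule would not discriminate at this size.

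**Conclusion.** The point holds as a gap in the analysis of a primary outcome: tests without an estimate, interval or bound. At 15 to 25 per arm, and for assumed control rates of 10% to 40%, the uncorrected chi-square test misses a 20-point excess in about 55% to 82% of trials. At 25 per arm the figure is about 45% for 5% versus 25% or 75% versus 95%; the Yates correction raises the range over all the rates tabulated to about 69% to 91%. The level, the event rates, the size of the harm and the form of the test are assumptions. The sample sizes and the absence of an interval come from the documents. A p-value alone would therefore say little about harm. The matter is worth correcting, but it does not show that the pilot is unsound or that its authors would equate non-significance with safety.

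**What to change.** In Table 1 and section 8:

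- For each adverse-event summary, report the rate in each arm and the risk difference with a small-sample 95% interval (Newcombe or exact). For event counts, report the difference between arms with a 95% interval.
- For serious events, report the exact upper 95% bound, including when none occur.
- Keep the chi-square and Mann-Whitney p-values as descriptive only, and state that a non-significant p-value is not evidence of similar safety.
- In the same edit, reconcile the summary of event counts, which is mean and standard deviation in Table 1 but median and interquartile range in section 8.

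Do not add a rule that acceptability is judged on the upper limit.

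The cost is a few sentences and a few lines of analysis code, with no new data. The downside is a safety statement that reads as less reassuring.

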There is inherent heterogeneity in the pediatric TBI population, and this study is designed to be *inclusive of the representative clinical population*, including those with pre-existing conditions. Given the ubiquitous use of melatonin in pediatric clinical care and research studies in a variety of pediatric populations with medical, developmental, and psychiatric disorders, no patients will be excluded for underlying medical conditions or concomitant medication use outside of the above exclusion criteria unless clinical judgement by the Attending Physician on the clinical care team would preclude use of melatonin for safety concerns.

Potential participants will be screened on arrival through the OHSU Emergency Department (all traumas, suspected traumas, and trauma referrals from other institutions are evaluated by the Trauma Surgery team in the Emergency Department per OHSU policy prior to admission). Medical records will be reviewed by the study team to determine eligibility; a waiver of consent under "Activities Preparatory to Research" for participant eligibility determination by research coordinators will be obtained. Research coordinators with the Trauma Research Group are present in the Emergency Department and are available to screen all TBI admissions for inclusion into active research studies 24hours/day. Screening information regarding inclusion/exclusion criteria will be retained for further analysis of recruitment outcomes.

c. Vulnerable Populations

The aims of this study are entirely focused on children ≥ 6 years to <19 years old. Inclusion of children is appropriate given the proposal focus on sleep outcomes in pediatric traumatic brain injury. Traumatic brain injury is a significant problem for children, including the leading cause of death and disability over 1 year of age. [name] is a Pediatric Critical Care physician with significant expertise in caring for children of all ages with critical illnesses, including traumatic brain injury, during the acute hospitalization. [name] also has unique expertise in the longitudinal care of these children after discharge, directing the Pediatric Critical Care and Neurotrauma Recovery Program. Age will be evaluated as a covariate in the analysis of both aims. Pregnant patients and prisoners are excluded.

d. Setting

Patients will be recruited from OHSU and Doernbecher Children's Hospital

e. Recruitment Methods

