- Children younger than 7 years: Assent is not required because the subjects are so young they cannot reasonably be consulted. However, a simple verbal explanation of the study procedures should be given if appropriate.

- Children ages 7 – 14 years: Researchers may obtain assent verbally and document this on the consent form or elsewhere in the research record, or researchers may ask the subject to sign an assent form after discussing the study with the subject at a level appropriate to the subject’s understanding. Researchers will use the OHSU assent template.
- Children ages 15 – 17 years: The subject may sign the consent form along with his or her parent(s) or guardian as documentation of assent. A separate assent form is not needed.

For non-English speaking participants, we have 24/7 available translators over the phone that will assist with the consent process. We will submit short consent form(s) for IRB review and approval as appropriate. An interpreter will assist with the initial consent process and subsequent study visits for all non-English speaking subjects.

Other than screening procedures described above, no modifications to the written consent process will be used.

6. Procedures Involved

Data Collection: Patients meeting inclusion criteria (see Eligibility Criteria) will be approached within 72hours of hospital admission to provide written consent and assent where appropriate. Parents will be asked to complete “baseline” assessments retrospectively to reflect the patient’s pre-injury status at the time of consent. Additional information will be collected by the study team from parents via survey and medical record review for demographic and clinical variables. Our goal recruitment and completion is for 30-50 patients.

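### The main SDSC regression does not name baseline SDSC, does not fix age and GCS group in the model, and does not say whether the unadjusted or an adjusted estimate is the main result.

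*Combined protocol and SAP*

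**What the plan says.** Section 8 (Data Analysis) examines effectiveness primarily through "linear regression to assess differences in the total SDSC score across treatment groups at 1-month". It adds that regression permits covariate control and that "covariates of particular interest will include age and TBI characteristics". It then provides for "Covariates identified in our initial descriptive analysis as significantly different between treatment groups, and covariates significantly associated with SDSC total score in bivariate analyses", which "will also be explored with multiple linear regression". No significance threshold is given for either screen.

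Section 5c says: "Age will be evaluated as a covariate in the analysis of both aims". Section 6 (Randomization) minimises on age and GCS severity group after an initial run of simple randomisation. Table 1 lists SDSC total at baseline and 30 days, marks it as a primary outcome within the exploratory effectiveness block, and gives the analysis as linear regression between arms without covariates. Under Section 6 (Data Collection), the baseline forms are completed by parents in retrospect, to reflect the child's "pre-injury status at the time of consent".

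The baseline characteristics that Section 8 lists for description are demographics, comorbidities and TBI features. SDSC is not among them. Secondary sleep outcomes "will be similarly evaluated with linear regression", apart from a count model for daytime sleep episodes, and "Results of these secondary analyses will be used as estimates for effect sizes in future intervention study design".

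**The concern.** Three decisions are left open: whether baseline SDSC enters the model, whether the two minimisation factors are fixed in it, and which estimate is the main result. The text allows two readings. One is an unadjusted main comparison with adjusted models as exploration. The other is a main model adjusted for age and TBI characteristics with an open list of additions; TBI characteristics alone covers at least severity, location and type.

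On either reading, baseline SDSC can stay out of the main result, and the precision it could add is then lost. If it comes in through a screen, the model is settled after the outcomes are known. The pilot is meant to inform a larger trial, and the secondary sleep outcomes analysed in the same way are to supply effect sizes, so the precision and identity of the estimate matter more here than its p-value.

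**Working it through.** The plan gives no SD, effect size, alpha or power for SDSC, so there is no figure of its own to reproduce.

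**Inputs.** Enrolment is 30 to 50 (Section 5a) and the retention goal is above 90% (Table 1). The lowest analysed number considered is 30 × 0.9 = 27; the others are 30, 50 × 0.9 = 45, and 50. The correlation r between baseline and 30-day SDSC is assumed to lie between 0.2 and 0.7.

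**1. Baseline SDSC alone against unadjusted.** Net of degrees of freedom, the relative change in the variance of the arm effect is (1 − r²)(N − 3)/(N − 4) − 1. For r = 0.5 and N = 27: 0.75 × 24/23 − 1 = −21.7%. For r = 0.5 and N = 50: 0.75 × 47/46 − 1 = −23.4%.

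**2. Would the plan's screens pick baseline SDSC?** Assume it is screened, at two-sided p < 0.05.

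- Association with SDSC: by Fisher's z the chance is about P(Z > 1.96 − atanh(r)·√(N − 3)). For r = 0.3, N = 27: atanh(0.3) = 0.310, times √24 = 1.52, so P(Z > 0.44) = 33%. For r = 0.3, N = 50: 0.310 × √47 = 2.12, so P(Z > −0.16) = 56%. Simulation gives 34 to 57%.
- Difference between arms: about 5% of trials (4 to 6% simulated) whatever r is, because randomisation leaves only chance differences. Age is picked in about 0 to 1%, since it is minimised.

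| r | Variance change, baseline alone (N = 27 to 50) | Picked by association screen (simulated) | Picked by between-arm screen |
|---|---|---|---|
| 0.2 | +0.2 to −1.9% | 16–31% | 4–6% |
| 0.3 | −5.0 to −7.0% | 34–57% | 4–6% |
| 0.5 | −22 to −23% | 79–97% | 4–6% |
| 0.7 | −47 to −48% | 99–100% | 4–6% |

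**3. A fixed model with arm, baseline SDSC, age and GCS group.** This was simulated with 5,000 trials per cell, no treatment effect and outcome SD 1. Allocation followed Section 6: simple until six per arm, then minimisation at 0.85. Assumed: age uniform from 6 to 19 and split at 12.5 years for minimisation; GCS mix 60/15/25%; age and severity effects either zero or 0.2 SD each. Entries are variance ratios to the unadjusted estimate, with simulation error of about 0.01 to 0.02.

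| r | No age or severity effect, N = 27–30 | Same, N = 45–50 | 0.2 SD effects, N = 27–30 | Same, N = 45–50 |
|---|---|---|---|---|
| 0.2 | 1.06–1.07 | 1.01 | 0.99–1.03 | 0.96–0.98 |
| 0.3 | 1.02–1.03 | 0.95–0.96 | 0.94–0.97 | 0.93–0.94 |
| 0.5 | 0.81–0.85 | 0.76–0.78 | 0.78 | 0.73 |
| 0.7 | 0.58 | 0.54–0.55 | 0.49–0.50 | 0.47–0.48 |

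**4. Does the choice of model move the estimate?** At N = 27 to 30 the unadjusted and fixed-model estimates from the same data differ by more than 0.2 SD in 30–35% of trials at r = 0.5 and 43–47% at r = 0.7. The unadjusted standard error is 2/√N, or 0.28 to 0.38 SD. A model with age, GCS group and baseline SDSC only when the association screen picks it behaves differently: at r = 0.5 to 0.7 its variance ratio agrees with the fixed model's within 0.01, and the two estimates differ by more than 0.2 SD in only 0 to 2.6% of trials.

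**The case against.** The strongest reply is that the plan already has a route to baseline SDSC. The association screen does target prognostic covariates, and where baseline matters most it would nearly always pick it. Step 4 bears this out. A reader might infer that the plan as written forfeits 22 to 48% of the variance, or that the reported estimate would often shift by more than 0.2 SD. The documents do not support that: those figures apply only if baseline SDSC stays out of the main result. Baseline SDSC is unnamed, not excluded, and the covariate list is open. What remains is that SDSC is missing from the listed baseline characteristics, so screening it is not assured, and a covariate that enters this way is chosen after outcomes are seen and only explored.

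It can also be said that the adjusted reading is the more natural one, because covariate control is mentioned straight after the regression. That may be so, but it brings in age and undefined TBI characteristics, not baseline SDSC, and still does not name the main estimate.

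Recalled pre-injury sleep may also correlate only modestly with sleep after a brain injury. That stands. At N = 27 to 30 and r = 0.2 to 0.3 the fixed model lies between 6% better and 7% worse than unadjusted.

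Finally, a reader might infer inflated type I error or lost power. Each fixed model held type I error at about 4 to 6%. The plan states no alpha or power for SDSC, calls the block exploratory and concedes that it is underpowered.

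**Conclusion.** The point holds in a limited form. Section 8 leaves baseline SDSC unnamed, does not fix the minimisation factors and does not identify the main estimate. If baseline SDSC stays out of that estimate, the loss is negligible at r = 0.2, 5 to 7% of variance at 0.3, and 22 to 48% at 0.5 to 0.7. If it enters through the association screen at r = 0.5 to 0.7, almost no precision is lost, but the model is not prespecified. Selection by between-arm significance rarely reaches baseline SDSC and does not look for prognostic covariates.

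The sizes rest on an assumed r, an assumed 0.05 screening threshold and, for the simulated results, the assumed age and severity mix. That the main model is not fixed rests on the text alone. This should be changed because the change is cheap; it does not threaten the feasibility aims of the pilot.

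**What to change.** In Section 8, name one main model: 30-day SDSC total on arm, baseline SDSC total, age and GCS group. Use the same form, with its own baseline value, for each other scale measured at both times. Drop covariate selection by between-arm significance. Label the unadjusted comparison, and any model with covariates chosen by association with SDSC, as sensitivity analyses. Align the Table 1 analysis column.

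The cost is wording only, with no new data. The model spends four more degrees of freedom (baseline 1, age 1, GCS group 2). At N = 27 to 30 this raises variance by up to about 7% if r is near 0.2 and neither age nor severity is prognostic.
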